## 7. SAFETY ASSESSMENTS

Expected adverse experiences for each study intervention are as follows:

EMindful Movement and Breathing

- Emotional discomfort
- Muscle soreness

Active Control

- Emotional discomfort

Each interventionist will monitor and note any adverse events experienced during the videoconferencing (e.g., patients' experience of disturbed breath, expression of physical/emotional discomfort, or request to discontinue the in-person intervention sessions). In addition, study staff will ask participants if they experienced any problems when doing the home practices and review notes from the home practice logs at follow-up visits. Instructors will have phone numbers for the triage nurse and Cancer Support Services available to give to patients as referrals if patients tell them about any clinical issues that arise. Study staff will also document in the electronic patient records using a telephone note if a referral number was provided.

Two or more adverse events attributable to the interventions will prompt modification of the protocol.

### 7.1 Specification of Safety Parameters

See previous section for safety parameters.

### 7.2 Methods and Timing for Assessing, Recording, and Analyzing Safety Parameters

Overall, risks related to the interventions in this study are considered to be minimal and are addressed in the protocol and consent form. The study employs gentle in bed movement, breathing and meditative practices or caring attention among people undergoing surgery for a suspected gynecologic malignancy. Similar yoga interventions have been conducted in patients with cancer with no published reports of adverse events, some which included participants during the perioperative period. The PI conducted an initial pilot study of 10 participants with the proposed yoga intervention implemented perioperatively in-person at WFBCCC from 05/2012 – 05/2013. There were no adverse events observed related to the yoga practice in this study.

The PI will monitor the safety of participants on an ongoing basis by inquiring about each participant's emotional and physical reactions during all regular study meetings with the interventionists and offer referrals by consulting with Co-Investigators when

appropriate. The PI will initially assess if the AE is related to the study interventions as definitely, probably, possibly or unrelated.

### **7.3 Adverse Events and Serious Adverse Events**

CTCAE term (AE description) and grade: The descriptions and grading scales found in the revised NCI Common Terminology Criteria for Adverse Events (CTCAE) version 4.0 will be utilized for AE reporting. All appropriate treatment areas should have access to a copy of the CTCAE version 4.0. A copy of the CTCAE version 4.0 can be downloaded from the CTEP web site (<http://ctep.cancer.gov>).

**‘Expectedness’: AEs can be ‘Unexpected’ or ‘Expected’ for expedited reporting purposes only.**

- **Attribution** of the AE:

- Definite – The AE is **clearly related** to the study intervention.
- Probable – The AE is **likely related** to the study intervention.
- Possible – The AE **may be related** to the study intervention.
- Unlikely – The AE is **doubtfully related** to the study intervention.
- Unrelated – The AE is **clearly NOT related** to the study intervention.

SAEs unequivocally due to disease progression are not considered SAEs for the purposes of this study and will not be reported as such.

Only AEs related to the study intervention or measures will be captured with the exception of unexpected grade 4 Grade 5 events, which will also be documented and reported.

AEs will be labeled according to severity, which is based on their impact on the patient. An AE will be termed “mild” if it does not have a major impact on the patient, “moderate” if it causes the patient some minor inconvenience, and “severe” if it causes a substantial disruption to the patient’s well-being.

AEs will be categorized according to the likelihood that they are related to the study intervention. Specifically, they will be labeled definitely unrelated, definitely related, probably related, or possibly related to the study intervention.

Interventionists will document and report solicited AEs including physical or emotional discomfort. Research staff will report AEs according to data safety monitoring plan. Events will be documented including date of event which will avoid double capture.

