- *Sleep Disturbance* will also be assessed with *actigraphy*, a non-intrusive alternative to the traditional polysomnography when monitoring sleep. The Actiwatch Spectrum model actigraph will be worn for up to 1 week before surgery and one week after surgery starting on postoperative day 1. This watch-like device measures rest/activity patterns in a natural setting, and provides summary measures of daily sleep activity. Sleep disturbance will be defined as a daily ratio of circadian disruption (the ratio of nighttime activity to daytime activity; higher scores show greater circadian disruptions). A similar device and the same ratio has been used in patients perioperatively. Participants will also self-report their bed and rising times daily.
- *Patient Provider Connection* will be measured with a 7-item short-form from the Healing Encounters and Attitudes Lists (HEAL) at the 4-week follow-up visit.
- *Clinical Factors.* Medications prescribed for pain, length of stay, any complications experienced, and other cancer treatments, will also be abstracted four weeks post-surgery.

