### **7.4 Reporting Procedures**

AEs reports will be distributed to the Independent Monitoring Committee (IMC) electronically via email.

The IMC will monitor and review adverse events and events that may be related to the intervention. This will include verification that, when indicated, these events have been reported to the appropriate agencies (e.g. IRB, NCCIH) and that such reports have been made in a timely manner. Non-serious adverse events will be reviewed on a quarterly basis by the IMC. The IMC will be notified of serious adverse events within 24 hours of occurrence and reviewed within 48 hours.

SAEs that are unanticipated, serious, and possibly related to the study intervention will be reported to the IMC, IRB, and the National Center for Complementary and Integrative Health (NCCIH) by sending the SAE Report Form via email (Appendix N: Adverse Event Form). The CCC-WFU Safety and Toxicity Reporting Committee (STRC) will also review unexpected grade 4 and all grade 5 events regardless of their attribution.

- Unexpected fatal or life-threatening AEs related to the intervention will be reported to the NCCIH Program Officer within 7 days. Other serious and unexpected AEs related to the intervention will be reported to the NCCIH Program Official within 15 days.
- Anticipated or unrelated SAEs will be handled in a less urgent manner but will be reported to the Independent Monitor(s), IRB, NCCIH, and other oversight organizations in accordance with their requirements. In the annual AE summary, the Independent Monitor(s) Report will state that they have reviewed all AE reports.

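### Section 7.3 captures only related AEs plus unexpected grade 4 and grade 5 events, but Section 7.4 requires unrelated SAEs to be reported; relatedness has no stated cut and is first judged by an unmasked PI

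*Combined protocol and SAP*

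**What the plan says.** - **Capture (Section 7.3).** "Only AEs related to the study intervention or measures will be captured". The same sentence then carves out some events by severity, and its wording for them is garbled: "with the exception of unexpected grade 4 Grade 5 events, which will also be documented and reported". I read the exception as unexpected grade 4 events and grade 5 events, in line with what Section 7.4 sends to the STRC whatever the attribution. Section 7.3 also removes SAE status from events that are clearly the result of disease progression.
- **Reporting (Section 7.4).** "Anticipated or unrelated SAEs will be handled in a less urgent manner but will be reported to the Independent Monitor(s), IRB, NCCIH". The list of recipients extends to further oversight bodies, and the duty is subject to what the recipients require. The IMC is to hear of serious adverse events within 24 hours, with no limit by attribution. The data review table in Section 10.3.2 lists SAEs for review per occurrence.
- **Who judges (Sections 7.2 and 4.3).** "The PI will initially assess if the AE is related to the study interventions as definitely, probably, possibly or unrelated". Under Section 4.3 the PI and the Project Manager learn the assignment after consent. Among study staff, the masking described in Sections 4.3, 6.2.3 and 9.5 covers those who collect outcome data.
- **Scales.** Section 7.2 has four levels. Section 7.3 first lists five, including Unlikely, and then says that events "they will be labeled definitely unrelated, definitely related, probably related, or possibly related to the study intervention".
- **Objective and analysis.** Section 1.2 (frequency of adverse events) and Section 9.6 (frequency of any adverse events) are not limited to related events. Section 9.2 names AE rates among the estimates that justify N = 31.
- **Complications (Section 6.2.4).** Under clinical factors, length of stay and "any complications experienced, and other cancer treatments, will also be abstracted four weeks post-surgery". Section 9.6 names neither for analysis.

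**The concern.** Two rules in adjacent sections disagree about the same events. Staff who follow Section 7.3 would not record an unrelated SAE that Section 7.4 tells them to report.

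The capture rule also makes the AE count depend on a causality judgement. For most events that judgement decides whether the event is recorded at all. It is made first by someone who knows the arm, and the threshold is not stated.

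What is at stake is the meaning of the AE frequency that the pilot hands to the next trial. Section 5.1 says that the eMMB is meant to help prevent ileus and deep venous thrombosis and to reduce pulmonary compromise. Complications of this kind that are judged unrelated are informative for that trial, and under the present rule they may not appear in the safety results.

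**Working it through.** **1. Capture against reporting**

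| Event | Captured under 7.3? | Position under 7.4 |
|---|---|---|
| Related SAE | Yes | Reported |
| Unrelated unexpected grade 4, or grade 5 | Yes, by the exception | STRC review; reported if serious |
| Unrelated SAE below grade 4 | No | To be reported, less urgently |
| Unrelated, expected grade 4 SAE | No | To be reported, less urgently |

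The last two rows are the conflict. The exception narrows it but does not remove it.

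**2. Attribution scales**

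| Level | 7.2 | 7.3, list of definitions | 7.3, labelling rule |
|---|---|---|---|
| Definite | Yes | Yes | Yes |
| Probable | Yes | Yes | Yes |
| Possible | Yes | Yes | Yes |
| Unlikely | No | Yes | No |
| Unrelated | Yes | Yes | Yes, as definitely unrelated |

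The scales differ by one level, Unlikely. Since no section says which levels count as related for capture, an event judged doubtfully related has no determinate handling.

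**3. The plan's own precision figures (Section 9.2)**

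- Two-sided 95% half-width at p = 0.5: 1.96 × √(0.5 × 0.5 / 31) = 0.176. The plan states 18 points.
- One-sided 95% lower limit at 80%: 0.80 − 1.645 × √(0.8 × 0.2 / 31) = 0.80 − 0.118 = 0.682. The plan states 68.2%.

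Both reproduce, and no figure is in dispute.

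**4. How far the count can move**

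Inputs: N = 31, randomized 1:1 (Section 9.2); background complication rate about 30% (Section 2.1). That this rate applies to the trial's mix of surgeries is an assumption.

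- Expected women with a complication: 0.30 × 31 = 9.3, or 0.30 × 15.5 = 4.65 per arm.
- If 9 of 31 were observed: 29%, exact 95% CI 14% to 48%.

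Let s be the share of complications judged related. The documents do not give s, so the table shows its full range. Recorded = 0.30 × s × 31; omitted = 0.30 × (1 − s) × 31; chance that none is recorded = (1 − 0.30s)^31.

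| s | Recorded | Omitted | Chance none recorded |
|---|---|---|---|
| 0% | 0 | 9.3 | 100% |
| 10% | 0.9 | 8.4 | 39% |
| 25% | 2.3 | 7.0 | 9% |
| 50% | 4.65 | 4.65 | 0.6% |
| 100% | 9.3 | 0 | below 0.01% |

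The table ignores the grade 4 and grade 5 exception, whose frequency is not given. It would move some events from omitted to recorded.

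If no event were recorded, the one-sided 95% upper limit would be 1 − 0.05^(1/31) = 9.2%, well below the 30% background rate. A reader could take that as reassurance about all adverse events when it describes only those that passed the capture rule.

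**5. Precision of a table by arm**

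With 15 and 16 women and 30% in each arm, the 95% half-width for the difference is 1.96 × √(0.21/15 + 0.21/16) = 0.32. Such a table can only be descriptive.

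**The case against.** Related-only capture is a disclosed choice in a study that Section 7.2 describes as minimal risk. This stands as a reason not to record every non-serious event. It does not reconcile Sections 7.3 and 7.4 on SAEs.

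The Section 7.4 duty is qualified by what the recipients require. Section 7.3 also refers to a data safety monitoring plan, and Section 7.4 to an adverse event form in an appendix; neither can be seen here. A reader might infer that the two rules cannot both be followed. That is not shown: another document may close the gap. The protocol text itself does not.

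A reader might infer that safety rests wholly on unmasked attribution. It does not. Visual analogue items before and after each session look for acute events (Section 6.2.4), interventionists and staff ask about problems (Section 7), and the IMC and the STRC review events (Section 7.4). The PI's judgement is called initial, and that it is unmasked is an inference from Sections 4.3 and 7.2 read together. Relatedness to movement or to diary writing can also hardly be judged without knowing which was received. All of this stands. Still, no masked adjudication is described, and outside the exception the capture rule keeps only events judged related. The practical answer is to show an attribution-free count beside the related one.

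A reader might infer that a planned safety comparison between arms would be biased. Section 9.6 specifies none. It plans an overall frequency and exploratory differences by surgery type and cancer type, and Section 9.2 says that the pilot is not designed to assess the effect of the eMMB.

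Finally, a reader might cite a prolonged stay as an unrelated SAE below grade 4. The documents shown give no definition of seriousness, so the example cannot be supported from them.

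**Conclusion.** The concern holds in a limited form. For unrelated SAEs outside the grade 4 and grade 5 exception, Section 7.4 sets a reporting duty and Section 7.3 has no matching capture. The passages must be reconciled. The attribution scales differ within Section 7.3 and between Sections 7.2 and 7.3, and no cut for related is stated. The planned AE frequency therefore depends largely, though not wholly, on a judgement first made by a PI who knows the arm.

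The possible size is from 0 to about 9 of 31 women with a complication left out of the AE counts. This assumes that the 30% background rate carries over to a trial that also enrolls women having less invasive surgery. A reader might take 9 as the number lost. It is an upper bound, reached only if every complication is judged unrelated and none meets the exception. It also counts complications, not SAEs, so it measures what the AE counts may miss and not the extent of the conflict between Sections 7.3 and 7.4.

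**What to change.** 1. **Sections 7.3 and 7.4:** make the capture rule agree with the reporting duty for SAEs.
2. **Sections 7.2 and 7.3:** use one attribution scale throughout, and state which levels count as related for capture and for the AE counts, including where Unlikely falls.
3. **Section 9.6:** beside the table of related AEs, add a descriptive table of the complications and length of stay already abstracted at four weeks, by arm and regardless of attribution, without formal testing. Label the related-AE table as such, so that a low count is not read as a low frequency of all adverse events.

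The cost is wording and one table from data in hand, with no new assessment. The downside is the recording of some unrelated SAEs, each with the IMC notification (24 hours) and review (48 hours) that Section 7.4 sets for serious events. The documents do not allow an estimate of how many there would be. The by-arm table will be imprecise at about 15 women per arm.

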### **7.4 Reporting Procedures**

AEs reports will be distributed to the Independent Monitoring Committee (IMC) electronically via email.

The IMC will monitor and review adverse events and events that may be related to the intervention. This will include verification that, when indicated, these events have been reported to the appropriate agencies (e.g. IRB, NCCIH) and that such reports have been made in a timely manner. Non-serious adverse events will be reviewed on a quarterly basis by the IMC. The IMC will be notified of serious adverse events within 24 hours of occurrence and reviewed within 48 hours.

SAEs that are unanticipated, serious, and possibly related to the study intervention will be reported to the IMC, IRB, and the National Center for Complementary and Integrative Health (NCCIH) by sending the SAE Report Form via email (Appendix N: Adverse Event Form). The CCC-WFU Safety and Toxicity Reporting Committee (STRC) will also review unexpected grade 4 and all grade 5 events regardless of their attribution.

- Unexpected fatal or life-threatening AEs related to the intervention will be reported to the NCCIH Program Officer within 7 days. Other serious and unexpected AEs related to the intervention will be reported to the NCCIH Program Official within 15 days.
- Anticipated or unrelated SAEs will be handled in a less urgent manner but will be reported to the Independent Monitor(s), IRB, NCCIH, and other oversight organizations in accordance with their requirements. In the annual AE summary, the Independent Monitor(s) Report will state that they have reviewed all AE reports.

## **7.5 Followup for Adverse Events**

AEs will be monitored by the IMC and the PI for recurrences, resolution, and ongoing toxicities that may be related to the intervention. Documentation and reporting for follow-up AEs will occur according to reporting procedures described in Section 7.4. The duration for follow-up will be for the length of the study period while participants are enrolled in the study. If non-serious adverse events are related to the interventions, then the protocol will be modified to avoid adverse events. If the frequency of non-serious adverse events is higher than anticipated or alters the benefit risk ratio, the study investigators, after conferring with IMC, will also modify the protocol. Two or more specific adverse events among participants will prompt modification of the protocol.

## **7.6 Safety Monitoring**

The Independent Monitoring Committee (IMC) for this study is comprised of the Wake Forest School of Medicine's Institutional Data and Safety Monitoring Board members who have expertise in clinical trial methodology and conduct, biostatistics, ethics, and clinical research. The Institutional Data and Safety Monitoring Board members are not part of the key personnel involved in this grant. They are qualified to review the patient safety data generated by this study because of their unique expertise in the areas of oncology, mental health/ethics and statistics.

Study progress and safety will be reviewed quarterly (and more frequently if needed). Progress reports, including patient recruitment, retention/attrition, and AEs will be provided to the Independent Monitor(s) following each of the quarterly reviews. An Annual Report will be compiled and will include a list and summary of AEs. In addition, the Annual Report will address (1) whether AE rates are consistent with pre-study assumptions; (2) reason for dropouts from the study; (3) whether all participants met entry criteria; (4) whether continuation of the study is justified on the basis that additional data are needed to accomplish the stated aims of the study; and (5) conditions whereby the study might be terminated prematurely. The Annual Report will be sent to the Independent Monitor(s) and will be forwarded to the IRB and NCCIH. The IRB and other applicable recipients will review progress of this study on an annual basis. The PI will also send copies of signed recommendations and comments from the Independent Monitor(s) or Chair of the IMC to the NCCIH Program Officer within 1 month of each monitoring review.

## **8. INTERVENTION DISCONTINUATION**

The intervention will be discontinued for a participant if: (1) the intervention is associated with an adverse effect for a specific participant (i.e., participant does not tolerate the intervention), (2) the participant no longer is interested or willing to receive the intervention or participate in the study, or (3) the participant's healthcare provider no longer recommends that the patient receive the intervention for medical reasons. The IMC and the principal investigator will review cases upon occurrence for discontinuation of intervention.

This study will be stopped prior to its completion if: (1) the intervention is associated with adverse effects that call into question the safety of the intervention; (2) difficulty in study recruitment or retention will significantly impact the ability to evaluate the study endpoints; (3) any new information becomes available during the trial that necessitates stopping the trial; or (4) other situations occur that might warrant stopping the trial. The PI will include an assessment of futility in the annual progress report to NIH and will consult with the study monitors to assess the impact of significant data loss due to problems in recruitment, retention, or data collection.

Participants will be followed with their permission if the study is discontinued. The duration of follow-up will be length of the proposed study. We will continue to document adverse events during the follow-up period.

## **9. STATISTICAL CONSIDERATIONS**

### **9.1 General Design Issues**

Inclusion of an active control group was chosen to account for Hawthorne effects, attention from a professional, and other non-specific effects. Alternate control groups considered include a wait-list control group or stretching. Specifically, the proposed empathic attention control was chosen to control for the non-specific effects of the intervention without including any of the proposed active intervention components.

Stratified randomized control design was selected for this study to enable tighter control over known influences on outcome. Statistical control via covariate analysis would not suffice.

1. **Primary Hypothesis:** We hypothesize that we will enroll at least 50% of eligible patients, participants will adhere to 70% of the interventions, and at least 70% of participants will complete study assessments and be retained in the study.

**Secondary:**

2. We will describe any adverse events reported as frequencies.
3. Assess descriptive data on proposed outcomes (i.e., pain [primary outcome - pain interference at week 2], sleep disturbances, psychological distress) for the next phase of study;

The Patient Reported Outcomes Measurement Information System (PROMIS) measure of pain of intensity (i.e., How would you rate your pain on average?), which has been validated for assessing pain on a numeric rating scale from 0 (no pain) to 10 (worst imaginable pain) “in the last day,” is the proposed primary outcome (at 2 weeks) for the future larger clinical trial that will be informed by the current study. Patient-reported pain is considered the ‘gold standard’ for pain assessment since pain is a subjective experience and PROMIS is supported by the NCCIH and National Cancer Institute.

4. Qualitatively assess acceptability to guide future study planning.

